### 1.2.2 Rationale for dose selection for Tenalisib

The safety and tolerability of Tenalisib has been established up to doses of 1200 mg BID and 800 mg TID. In an ongoing US study, Tenalisib 800 mg BID (Fasting) is established as a MTD dose in patients with T-cell lymphoma. Therefore, Tenalisib (800 mg BID) is considered for this study.

## 1.3 Benefit and Risk

It is expected that proposed monotherapy has the potential to improve response rates in the proposed patient population. However, all the patients in clinical trials generally cannot expect to receive direct benefit from treatment during participation, as clinical trials are designed to provide information about the safety and effectiveness of an investigational

medicine. Additional details regarding specific benefits and risks for subjects participating in this clinical trial may be found in the accompanying IB and Informed Consent documents.

## **2 TRIAL OBJECTIVES**

### **2.1 Primary Objective**

- To assess the anti-tumor activity of Tenalisib, as determined by the Objective Response Rate (ORR), Duration of Response (DoR) and Progression Free Survival (PFS).

### **2.2 Secondary Objective**

- To characterize safety and tolerability of Tenalisib in patients with iNHL.

## **3 TRIAL DESIGN**

### **3.1 Trial End Points**

- **Efficacy:**

- **ORR** is defined as sum of CR and PR rates and will be assessed according to the Lugano Classification for initial evaluation, staging, and response assessment of Non-Hodgkin lymphoma. (Cheson-2014)
- **CR rate** will be assessed according to the Lugano Classification for initial evaluation, staging, and response assessment of non-Hodgkin lymphoma.
- **DoR** is measured from the initial response to disease progression or death.
- **PFS** is defined as the time of the first dose of Tenalisib to disease progression or death.

- **Safety:**

- Adverse Event (AE), Grade 3/ 4 AEs, Serious and fatal Adverse Event (SAE), graded using NCI CTCAE Version 5.0.

### **3.2 Design of Trial**

The study is designed as a Phase II, open label, two parts study in relapsed/refractory iNHL patients. The mandatory Part 1 of the study will assess the efficacy and safety of Tenalisib in 20 patients with iNHL. After all patients enrolled in Part 1 have had the opportunity to provide at least three tumor outcome assessments, the Data Review Committee (DRC) will evaluate the efficacy (anti-tumor activity) and safety results for each of the subtypes (e.g. FL, MZL or WM). If the committee believes there are potential clinically meaningful responses for certain subtype, the committee will recommend initiation of Part 2 to evaluate efficacy and safety for that subtype. If not, the study will be terminated without initiating Part 2. The sample size for Part 2 will be derived based on the outcome from Part 1. Data from Part 1 will not be included in the analysis of Part 2 of the study.

The study treatment Tenalisib (800 mg BID) will be administered orally in 28-days of cycle over a period of 8 months in absence of definitive disease progression or unacceptable toxicity. Treatment will be continued in patients experiencing clinical benefit until the

occurrence of definitive disease progression, unacceptable toxicity, or withdrawal from the study due to investigator decision or other reasons; maximum for up to 24 months.

The efficacy response will be evaluated on Weeks 8 (C3D1± 7 days), Weeks 16 (C5D1± 7 days) and then every 12 weeks thereafter, and/ or at the EOT or as clinically indicated (if clinical progression is suspected or for confirmation of complete response/disease progression). The details of the study procedures are given in Schedule of Events.

Group	N	Patient population	Tenalisib
Part 1	20	Refractory/ relapsed iNHL.	800 mg BID in 28-Days Cycle for 8 Cycles 
Part 2	The sample size will be derived based on the outcome from Part 1	Refractory/ relapsed iNHL patients of one of the specific subtype (e.g. FL, MZL, WM)	800 mg BID in 28-Days Cycle for 8 Cycles 

Post cycle 8, treatment will be continued in patients experiencing clinical benefit up to 24 months unless progression of disease or toxicity warranting discontinuation of therapy. The decision to continue the treatment will be determined by the PI after consultation with Sponsor on case to case basis.

### 3.3 Data Review Committee (DRC)

The DRC will be constituted by the sponsor in consultation with PI and will consist of PI, sponsor representative, sponsor's medical expert, medical monitor, and a statistician. The DRC will meet and review the safety and efficacy data at regular interval and as required by the sponsor/investigator to assess the safety and tolerability of study drug.

After all patients enrolled in Part 1 have had the opportunity to provide at least three tumor outcome assessments, the DRC will evaluate the efficacy (anti-tumor activity) and safety results for each of the subtypes. If the committee believes there are potential clinically meaningful responses for certain subtype, the committee will recommend initiation of Part 2 to evaluate efficacy and safety for that subtype.

### 3.4 Randomization and Blinding

This is a non-randomized, open label study.

### 3.5 Investigational Medicinal Product

#### 3.5.1 Dosage form and strengths

Investigational Product	Dosage form, strength	Manufacturer
Tenalisib	Tablets; 200 mg and 400 mg.	STA Pharma Co. Ltd.

**Note:** Please refer Investigator's brochure for additional information of Tenalisib.

### **3.5.2 Labeling, packaging and supply**

Tenalisib will be supplied by STA Pharma Co. Ltd. through Rhizen Pharmaceuticals S.A. Tenalisib will be available as 30 tablets per bottle. All trial drugs must be kept in a secure place at below 25°C (77°F), protected from moisture.

### **3.5.3 Preparation and administration of Investigational Products**

At each visit, patients will be dispensed sufficient quantity of Tenalisib until the next visit. Study drug compliance should be reviewed with the patient at the beginning of each new treatment cycle. Study drug compliance must be documented, including missed doses and subject re-education and dose administration.

#### **Guideline for administration of Tenalisib:**

- Method of Administration: Tenalisib will be administered orally twice daily.
- Pre-medications: None. No routine prophylactic anti-emetics or pre-medications should be given outside of protocol requirements. However, these medications may be administered for the treatment of symptoms (see Section 5.3).
- Tenalisib tablets will be self-administered orally twice daily one hour before a major meal (e.g. breakfast and dinner). Patients should not consume food during this one-hour period.
- Tenalisib tablets should be taken at approximately same time each day. Tablets should be swallowed; and should NOT be crushed or chewed.
- If a dose of Tenalisib is missed, it should be taken as soon as possible on same day with an interval of 8 hrs between two doses. If it is missed for the entire day, it should not be repeated. If vomiting occurs, no attempt should be made to replace the vomited dose.
- Study drug compliance should be reviewed at the beginning of each new treatment cycle. Missed doses should be documented.

### **3.5.4 Accountability of Investigational Products**

The PI/ designee are responsible for accountability of all trial drug supplies (used/unused) at the site. The study monitor will verify receipt of investigational product at the sites during monitoring visit(s), and will conduct an inventory of remaining clinical trial supplies at the site close-out visit. All trial drug inventories must be made available for inspection by the monitor, sponsor representatives and regulatory agency inspectors/monitor upon request.

Following monitor verification, returned or expired trial drugs can be destroyed according to local institutional policy with sponsor pre-approval of a site-specific destruction policy. Certificate of destructions must be filed at the site and in Trial Master File.

### **3.5.5 Precautions and risks associated with Investigational Products**

- Monitoring of liver enzymes and levels of TSH, T3, and T4 in subjects receiving Tenalisib is recommended based on target organ toxicity. Patients should be monitored for increased ALT/AST, skin rash, neutropenia as these events are reported with Tenalisib. Monitor patients for signs and symptoms of these events and interrupt

Tenalisib for Grade 3 or higher event. In addition, enteritis (colitis), pneumonia/pneumonitis as these events are reported with other PI3K inhibitors.

- Tenalisib may cause serious infections that may include sepsis and other infections. Monitor patients for signs and symptoms of infection and interrupt Tenalisib for Grade 3 or higher infection.
- Tenalisib elicits no photo instability upon exposure to ultraviolet (UV) radiations. However, in absence of in vitro data, possibility of photo-toxicity with Tenalisib cannot be ruled out.
- Tenalisib demonstrated moderate to high inhibition of CYP3A4 enzymes. Therefore, concomitant administration of Tenalisib with CYP3A4 substrates (e.g. calcium channel blockers, warfarin, carbamazepine, macrolide antibiotics, lovastatin, simvastatin, terfenadine) may reduce clearance of these drugs increasing the risk of adverse events. Similarly, as Tenalisib is inhibited by CYP3A4/5 and CYP2C9, there is possibility of drug interaction with inhibitors or inducers of CYP3A4 and CYP2C9. If concomitant treatment of these drugs are clinically warranted, careful observation of the patient is advised. Raised INR has been reported with concomitant warfarin administration. Therefore, use of heparin or warfarin is generally avoided. Low molecular weight heparin (LMWH) is advised for prophylaxis and treatment of venous thrombosis.
- Strong inhibitor or inducers should be avoided as directed in Section on prohibited medication. Please refer to the recent Investigator Brochure for additional safety information.
- In absence of reproductive toxicity and genotoxicity data, the study participants should be advised to follow post treatment contraceptive measures.

### **3.6 The Expected Duration of Subject Participation and Follow-up**

The expected duration of subject participation in the study will be 8 months. Treatment will be continued in patients experiencing clinical benefit up to 2 years unless progression of disease or toxicity warranting discontinuation of therapy. The decision to continue the treatment will be taken by PI after consultation with sponsor on case to case basis.

### **3.7 Study Stopping Rules**

#### **Efficacy:**

After all patients enrolled in Part 1 have had the opportunity to provide at least three tumor outcome assessments, the DRC will evaluate the efficacy (anti-tumor activity) and safety results for each of the subtypes. If the committee believes there are potential clinically meaningful responses for certain subtype, the committee will recommend initiation of Part 2 to evaluate efficacy and safety for that subtype. Else, the study will be terminated.

**Safety:** The DRC will continue to monitor safety of Tenalisib (or toxicity trends that may be of concern) at interval of approximately 3 months from initiation of study until the completion of the study. In the event of one (1) death attributed to the study drug, study accrual will be suspended pending further investigation, and will only be resumed at the recommendation of the DRC. The DRC will have discretion to terminate the trial if an additional death occurs that can be attributed to the study drug.

Sponsor reserves the right to terminate the study in the interest of patient safety, for non-compliance with the protocol, lack of recruitment or any other administrative reasons. The sponsor and PIs will notify the regulatory authority and respective IRB respectively if the trial terminates early, with a justification for the early termination.

10. Male patients willing to use adequate contraceptive measures throughout the study period and for 12 weeks after the last dose of Tenofovir.
11. Willingness and ability to comply with trial and follow-up procedures, give written informed consent.

#### **4.2 Exclusion Criteria**

1. Histologically confirmed diagnosis of follicular lymphoma grade 3b or transformed disease or chronic lymphocytic leukemia (CLL).
2. Patients receiving cancer therapy (i.e., chemotherapy, radiation therapy, immunotherapy, biologic therapy, hormonal therapy, surgery and/or tumor embolization) or any cancer investigational drug within 3 weeks (21 days) or 5 half-lives (whichever is shorter) prior to C1D1. Corticosteroids (prednisone or equivalent) at a dose of < 20 mg daily are allowed. Corticosteroid should be stabilized for at least 1 week prior to C1D1.
3. Autologous hematologic stem cell transplant (Auto-SCT) within 3 months from C1D1. Patients must not have active graft versus-host disease;
4. History of an allogeneic bone marrow transplant (Allo-SCT)
5. Active hepatitis B or C infection. (All subjects must be screened for hepatitis B and C up to 28 days prior to C1D1 using the hepatitis viral panel. Subject positive for HBsAg or HBcAb will be eligible if they are negative for HBV-DNA. Subject positive for HCV IgG will be eligible if they are negative for HCV-RNA);
6. Known history of human immunodeficiency virus (HIV) infection;
7. Evidence of ongoing severe systemic bacterial, fungal or viral infection;
8. Known primary central nervous system lymphoma or known intracranial involvement, leptomeningeal metastases or spinal cord compression due to disease or any preexisting neurologic manifestations;
9. Known history of severe drug-induced liver injury, alcoholic liver disease, primary biliary cirrhosis, ongoing extrahepatic obstruction caused by stones, cirrhosis of the liver or portal hypertension;
10. Patient with any severe and/or uncontrolled medical conditions or other conditions that could affect their participation in the study as per investigator's judgement;
11. Patient with symptomatic, or history of documented congestive heart failure (NY Heart Association functional classification III-IV);
12. Patient with angina not well-controlled by medication;
13. Patient with poorly controlled or clinically significant atherosclerotic vascular disease (including cerebrovascular accident, transient ischemic attack or have angioplasty, cardiac or vascular stenting) in the past 6 months;
14. Prior exposure to drug that specifically inhibits PI3K (e.g. Idelalisib, Copanlisib, Duvelisib and Umbralisib);
15. Previous or concurrent malignancy that is distinct in primary site or histology from indolent B-cell NHL within 3 years of study enrollment EXCEPT for adequately treated basal, squamous cell carcinoma or non-melanomatous skin cancer, carcinoma in situ of the cervix, superficial bladder cancer not treated with intravesical chemotherapy or BCG within 6 months, localized prostate cancer with PSA <1.0 mg/dL on 2 consecutive

measurements at least 3 months apart with the most recent one being within 4 weeks of study entry;

16. Patients with seizure disorder requiring medication;
17. Unresolved toxicity higher than CTCAE grade 1 (NCI-CTCAE version 5.0) attributed to any prior therapy/procedure excluding alopecia;
18. Myeloid growth factors or red blood cells/ platelet transfusion within 14 days prior to C1D1;
19. Administration of any of the following within 1 week prior to C1D1:
  - a. **Strong inhibitors or inducers of CYP3A4**, including grapefruit products, herbal medications.
  - b. **Strong inhibitors or inducers of CYP2C9**, including herbal medications.
  - c. Substrates of CYP3A4 enzyme with a **narrow therapeutic range** (e.g. Warfarin and phenytoin)
20. Pregnant or lactating woman;
21. Inability or unwillingness to comply with study and/or follow-up procedures outlined in the protocol;
22. Concurrent condition that in the investigator's opinion would jeopardize compliance with the protocol.

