	
 
13. Patient with poorly controlled or clinically significant atherosclerotic vascular disease (including cerebrovascular accident, transient ischemic attack or have angioplasty, cardiac or vascular stenting) in the past 6 months;
 
14. Prior exposure to drug that specifically inhibits PI3K (e.g. Idelalisib, Copanlisib, Duvelisib and Umbralisib)
 
15. Previous or concurrent malignancy that is distinct in primary site or histology from indolent B-cell NHL within 3 years of study enrollment EXCEPT for adequately treated basal, squamous cell carcinoma or non-melanomatous skin cancer, carcinoma in situ of the cervix, superficial bladder cancer not treated with intravesical chemotherapy or BCG within 6 months, localized prostate cancer with PSA <1.0 mg/dL on 2 consecutive measurements at least 3 months apart with the most recent one being within 4 weeks of study entry;
 
16. Patients with seizure disorder requiring medication.
 
17. Unresolved toxicity higher than CTCAE grade 1 (NCI-CTCAE version 5.0) attributed to any prior therapy/procedure excluding alopecia.
 
18. Myeloid growth factors or red blood cells/ platelet transfusion within 14 days prior to C1D1.
 
19. Administration of any of the following within 1 week prior to C1D1:             
 
a. Strong inhibitors or inducers of CYP3A4, including grapefruit products, herbal medications.
 
b. Strong inhibitors or inducers of CYP2C9, including herbal medications.
 
c. Substrates of CYP3A4 enzyme with a narrow therapeutic range (e.g. Warfarin and phenytoin)
 
 
 
20. Pregnant or lactating woman;
 
21. Inability or unwillingness to comply with study and/or follow-up procedures outlined in the protocol;
 
22. Concurrent condition that in the investigator's opinion would jeopardize compliance with the protocol.
 

Estimated Study duration
	
Part 1: Approximately 12 months for accrual plus 8 months of follow up                  Part 2: To be determined.

Assessment of Response
	
Response assessments will be performed as per Lugano Classification (Cheson criteria 2014) at C3D1 (<math>\pm</math> 7 days), C5D1 (<math>\pm</math> 7 days) and approximately every 12 weeks thereafter (<math>\pm</math> 7 days), and/ or at the EOT.

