## **9.2 Determination of Sample Size**

Since study Part 1 was exploratory in nature. The sample size for Part 1 is not based on statistical considerations. After all patients enrolled in Part 1 had the opportunity to provide at least three tumor outcome assessments, the DRC will evaluate the efficacy and safety results for each of the subtypes. If the committee believes there are potential clinically meaningful benefits for certain subtype, the committee will recommend initiation of Part 2 to evaluate efficacy and safety for that subtype. The sample size for Part 2 will be derived based on ORR data from Part 1.

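### The PSA limit in exclusion 15 is printed as 1.0 mg/dL, which is 10,000 ng/mL, so as written it can hardly screen anyone out of the localized prostate cancer exception

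*Protocol*

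**What the plan says.** Item 15 of Protocol Section 4.2 excludes a "Previous or concurrent malignancy that is distinct in primary site or histology from indolent B-cell NHL within 3 years of study enrollment EXCEPT" for a short list of cancers. One of these is "localized prostate cancer with PSA <1.0 mg/dL on 2 consecutive" occasions, and the timing of these is then fixed: "measurements at least 3 months apart with the most recent one being within 4 weeks of study entry". The synopsis carries the same figure and unit: "1.0 mg/dL on 2 consecutive measurements at least 3 months apart with the most recent one being within 4 weeks of study entry".

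No other PSA limit, unit, range or assay appears in either document. PSA is not in the Schedule of Events (Protocol Table 1) or the laboratory list (Protocol Table 2). The amendment history names changes to inclusion 7 and exclusion 9 but none to exclusion 15.

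Three other criteria bear on the same patients:

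- Exclusion 2 covers "Patients receiving cancer therapy (i.e., chemotherapy, radiation therapy, immunotherapy, biologic therapy, hormonal therapy, surgery and/or tumor embolization") within 21 days or 5 half-lives of C1D1, whichever is shorter.
- Exclusion 10 covers a "Patient with any severe and/or uncontrolled medical conditions or other conditions that could affect their participation in the study", as the investigator judges.
- Exclusion 22 covers concurrent conditions that the investigator thinks would jeopardize compliance.

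On the analysis side, SAP 7.2 gives enrolment of an ineligible subject as an example of a major deviation, and major deviators leave the per-protocol (PP) population. SAP 11 has the medical monitor decide on PP inclusion before database closure.

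**The concern.** Among the listed exceptions, only the prostate one carries a biomarker cut-off. Two values, a minimum spacing and a recency rule suggest that the drafters wanted evidence of controlled disease. A limit that almost any result satisfies cannot supply that evidence, however well the measurements are timed.

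Two things would be at stake. First, a man whose localized prostate cancer is not biochemically controlled could satisfy the exception on its literal terms. Death from any cause is a PFS event (SAP 10.5.3), and PFS is part of the primary objective. Second, sites could differ: one applies the unit as printed, another silently substitutes the unit on its laboratory report. The same patient would then be eligible under one reading and a major deviator under the other, so PP membership would turn on an undocumented choice.

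**Working it through.** **Inputs.** The limit is below 1.0 mg/dL on both measurements (Protocol Section 4.2 item 15, and the synopsis). The conversion factors are 1 mg = 1,000,000 ng and 1 dL = 100 mL. The protocol gives no derivation of the limit, so there is no plan calculation to reproduce.

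**Conversion.** Limit in ng/mL = 1.0 × 1,000,000 / 100 = 10,000. In the other direction, 1 ng/mL = 100 / 1,000,000 = 0.0001 mg/dL.

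**Which values pass.** The PSA values below are assumed, chosen to span a wide range. The last column reads the same number in ng/mL. It is there only to show how far apart the two readings are and does not propose a limit.

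| PSA (ng/mL) | In mg/dL | Below 1.0 mg/dL? | Below 1.0 ng/mL? |
|---|---|---|---|
| 0.5 | 0.00005 | yes | yes |
| 1 | 0.0001 | yes | no |
| 4 | 0.0004 | yes | no |
| 20 | 0.002 | yes | no |
| 100 | 0.01 | yes | no |
| 1,000 | 0.1 | yes | no |
| 9,999 | 0.9999 | yes | no |
| 10,000 | 1.0 | no | no |

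The two readings differ by 10,000 / 1 = 10,000-fold and disagree for every value from 1 ng/mL up to, but not including, 10,000 ng/mL.

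**What else constrains the exception.** The disease must still be localized, which concerns extent and not biochemical control. Two measurements with the stated timing are still needed. The list of exceptions opens with a qualifier about adequate treatment, but the sentence does not make clear whether that reaches prostate cancer. Exclusion 2 catches recent treatment, not untreated disease. Exclusions 10 and 22 are discretionary and contain no PSA figure. These narrow the gap, but none replaces the numeric limit.

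**Reach into the analysis.**

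- *mITT (SAP 7.1, primary for efficacy):* defined by at least one dose and one post-baseline efficacy assessment. Eligibility does not enter, so the reading of the unit changes nothing.
- *PP (SAP 7.2, also used for efficacy under SAP 10.5):* a patient's membership can change with the reading. SAP 7.2 drops the PP outputs if PP and mITT contain the same patients, so a single reclassification could also decide whether those outputs are produced.
- *Sample size and error rates:* unaffected. Protocol 9.2 states "The sample size for Part 1 is not based on statistical considerations", and SAP 9.1 sets no formal hypotheses.

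**The case against.** The strongest reply is that the documents do not contradict themselves. Synopsis and body agree, and calling the unit mistaken relies on general knowledge of how large PSA values are. That is fair as to the source of the judgement, and the assumption should be stated openly. The conversion itself needs no outside fact, and the agreement of the two places only means that neither corrects the other.

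A reader might go further in three ways that the documents do not support:

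- *That item 15 lets active second cancers in generally.* It does not. Other distinct malignancies within 3 years remain excluded apart from listed exceptions that this unit does not touch.
- *That the unit is what lets a rising PSA through.* Item 15 has no rule on trend under any unit. A rise from 0.1 to 0.9 ng/mL would also pass a limit of 1.0 ng/mL.
- *That the results are distorted by a known amount.* One patient would be 1/20 = 5% of the planned Part 1, but nothing shows that any patient had prostate cancer or used the exception.

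More of the reply stands on consequence. The primary population is untouched, and the medical monitor's review of deviations gives a point at which the reading can be settled. Appendix C asks that new PET foci be consistent with lymphoma and allows biopsy in doubt, which limits confusion on imaging. The SAP notes under Section 5.1 say that the study is closed and Part 2 will not be performed, so correcting the text will not alter future entry to this trial.

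**Conclusion.** The point holds for the PSA limit in the localized prostate cancer exception, and for nothing wider. As printed, the limit is 10,000 ng/mL. If PSA values lie in the usual clinical range, which is an assumption because the documents give none, it screens out almost no one and can admit localized disease that is not biochemically controlled.

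This is more than a slip in background text: it is an operative entry rule that gives the wrong answer when followed literally. The practical effect is probably small. Sites may have corrected the unit themselves, and the number of affected patients is unknown and may be zero. What remains is an eligibility check, consistent PP classification and an accurate record.

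**What to change.** 1. The sponsor confirms the intended unit and limit. The text alone cannot settle either, and this review does not choose one.
2. Correct item 15 in both the synopsis and Section 4.2 or, as the study is closed, issue a documented clarification. The item should not be carried unchanged into later protocols.
3. Check whether any enrolled patient entered under this exception. The eligibility, prior-therapy and cancer-diagnosis listings (SAP 12) and the medical history listing (SAP 10.3) are the place to start. PSA is not a scheduled laboratory test, so source records may be needed for the values.
4. If there is such a patient, apply the confirmed reading when classifying the deviation and deciding PP membership under SAP 7.2 and 11, and record the reason.

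The cost is an administrative amendment or note to file plus a short source check. An amendment would need sponsor and investigator approval and IRB/IEC submission under Protocol 11.1, which makes the clarification the lighter route. No analysis method changes, and mITT results do not change.
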